# 2.3.3 Exploratory Endpoints

- HPV IgG GMC by ELISA and GMT by PBNA at baseline, at the time of second dose, and one month after the second dose (for immunologic bridging and kinetic modeling)
- HPV IgG GMC by ELISA following a single dose of Gardasil® or Cecolin® at 6, 12, and 24 months

# 3 STUDY DESIGN

This randomized, active-comparator controlled, open-label Phase 3 study will enroll approximately 1025 girls aged 9 to 14 years in one country in Africa (Ghana) and one country in South/Southeast Asia (Bangladesh).

Subjects will be randomized 1:1:1:1:1 to receive Cecolin® at 0 and 6 months, 0 and 12 months, or 0 and 24 months, Gardasil® at 0 and 6 months, or Gardasil® at 0 months and Cecolin® at 24 months (see Figure 1). For each arm, blood will be collected for immunologic testing at baseline and one month following second dose. Additional blood collections will occur immediately prior to the administration of the 6-month, 12-month or 24-month dose for immunobridging to other published and ongoing trials and 24 months after the first dose in groups 1 and 4 for noninferiority comparison.

Girls of target age will be identified, and their parents contacted to attend an informational session for individual discussion, informed consent, and randomization.

The study will be conducted by two research groups in two selected countries Bangladesh and Ghana.

The vaccination arms will be divided into 5 groups as below:

Group 1: Cecolin® 0 and 6 months

Group 2: Cecolin® 0 and 12 months

Group 3: Cecolin® 0 and 24 months

Group 4: Gardasil® 0 and 6 months (control)

Group 5: Gardasil® 0 months and Cecolin® 24 months

# 4 STUDY POPULATION

# 4.1 Description of Study Population

The study population will include approximately 1025 girls (205 per arm) 9-14 years of age. The study will have two sites recruited from one country in Africa (Ghana) and one country in South/Southeast Asia (Bangladesh).

Final eligibility determination will depend on the results of the medical history, clinical examination, fulfillment of all the inclusion and absence of any of the exclusion criteria, and appropriate understanding of the study and completion of the consent process by parents of all participants and assent of adolescent participants.

Investigators should always use good clinical judgment in considering a participant's overall fitness for inclusion in the trial. Some participants may not be appropriate for the study, even if they meet all the eligibility criteria. In addition, the participants should reside in reasonable proximity to the study site, without plans to leave the area prior to the end of the study. A sufficient number of healthy young adolescents will be screened, with consent, to randomize the required sample size for the study.

### 4.2 Inclusion Criteria

- 1. A healthy (determined by investigator's assessment following medical history and physical examination) female between the ages of 9 14 years (all inclusive) at time of enrollment
- 2. Ability and willingness to provide parental consent and, if applicable based on local incountry regulations, participant assent.
- 3. Parent/LAR provides informed consent
- 4. Anticipated ability and willingness to complete all study visits and evaluations
- 5. Living within the catchment area of the study without plans to move during the conduct of the study

### 4.3 Exclusion Criteria

- Presence of fever or acute disease on the day of vaccination (oral or axillary temperature ≥38°
   C)
- If participants have childbearing potential, must not be breastfeeding or confirmed pregnant.
   Women of childbearing potential is defined as any woman or adolescent who has begun menstruation.
- 3. Receipt of an investigational product within 30 days prior to randomization or planning to participate in another research study involving investigational product during the conduct of this study
- 4. Receipt of blood and/or blood products (including immunoglobulin) in 3 months prior to any dose of vaccination or blood sampling
- 5. Receipt of a live virus vaccine (varicella virus containing vaccine, any measles, mumps, or rubella virus containing vaccine such as MMR, or yellow fever vaccine but not including live attenuated influenza virus vaccine) 4 weeks prior and after each dose of HPV vaccine

- 6. History of any physical, mental, or developmental disorder that may hinder a participant's ability to comply with the study requirements
- 7. Any malignancy or confirmed or suspected immunodeficient condition such as HIV infection, based on medical history and physical examination
- 8. Receipt of or history of receipt of any medications or treatments that affect the immune system, such as immune globulin, interferon, immunomodulators, cytotoxic drugs or other drugs known to be frequently associated with significant major organ toxicity since six months prior to the first HPV vaccine dose. Receipt of long-term (greater than or equal to 2 weeks) potentially immunosuppressive corticosteroid use within six months prior to HPV vaccine dose 1 and enrollment or anticipated receipt during the study period. Specifically, potentially immunosuppressive corticosteroids are any parenteral corticosteroid, high dose (>800 mcg/day) beclomethasone dipropionate or equivalent medication. Nasal and topical steroids are allowed.
- 9. Allergies to any components of the vaccine
- 10. Current or former participation in HPV vaccine related research.
- 11. Prior receipt of an investigational or licensed HPV vaccine
- 12. Any other condition(s) that in the opinion of the investigator would jeopardize the safety or rights of a participant participating in the trial or would render the participant unable to comply with the protocol.

# 4.4 Continued Eligibility Confirmation for Subsequent Vaccination

The following events constitute absolute contraindications to HPV vaccination. If any of these events occur during the study, the participant must not receive additional doses of the vaccine but should be appropriately followed up for safety by the investigators.

- Hypersensitivity reaction following the administration of the study vaccine.
- Detection of one or more of the exclusion criteria during dosing period. (except fever)
- Significant intercurrent illness.
- Protocol deviation rendering data unusable or increasing risk for subsequent vaccinations.
- Receipt of HPV vaccine outside of study.
- Any condition which, in the opinion of the investigator, might jeopardize the safety of the
  participant or interfere with the evaluation of the study objectives.

The following events constitute contraindications to administration of the study vaccine at that point in time; if any of these events occur at the time scheduled for vaccination, the participant may be vaccinated at a later date, within the time window specified in the protocol, or withdrawn at the discretion of the Investigator.

- Acute disease and / or fever at the time of vaccination. (temporary deferment)
  - Acute disease is defined as the presence of a moderate or severe illness with or without fever. All vaccines can be administered to persons with a minor illness such as mild upper respiratory infection without fever.

- o Fever is defined as temperature ≥38°C on oral or axillary setting.
- Gastroenteritis within 72 hours preceding the study vaccine administration (temporary deferment).

For participants with temporary exclusion criteria (acute illness or gastroenteritis) prior to receiving the subsequent dose of study vaccine, vaccination may be deferred within the defined vaccination windows. The study vaccine can be administered outside the study window based on investigators discretion and a protocol deviation will be filed for the same. If subsequent study vaccinations are discontinued, every effort will be made to encourage the participants to remain in the study for safety follow up.

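### Protocol 4.4 exempts only fever from its permanent bar on dose 2, so time-limited live-vaccine and blood-product exclusions end a girl's regimen, and acute disease is both barred and deferred

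*Protocol*

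**What the plan says.** Protocol 4.4 has two lists. The first names absolute contraindications. If one occurs, "the participant must not receive additional doses of the vaccine". One entry is "Detection of one or more of the exclusion criteria during dosing period. (except fever".

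Three of the 12 exclusion criteria in Protocol 4.3 are tied to the time around each dose:

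- Criterion 1: "Presence of fever or acute disease on the day of vaccination".
- Criterion 4: "Receipt of blood and/or blood products (including immunoglobulin) in 3 months prior to any dose of vaccination or blood sampling".
- Criterion 5: live virus vaccine "4 weeks prior and after each dose of HPV vaccine".

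The second list in 4.4 covers conditions that only postpone the dose. It contains "Acute disease and / or fever at the time of vaccination. (temporary deferment" and gastroenteritis in the preceding 72 hours. The closing paragraph is equally narrow: "For participants with temporary exclusion criteria (acute illness or gastroenteritis) prior to receiving the subsequent dose of study vaccine, vaccination may be deferred". It then adds that "The study vaccine can be administered outside the study window based on investigators discretion", with a deviation filed.

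Eligibility is checked again before dose 2 in every group (Protocol 6.2.5, 6.2.9, 6.2.12 and Appendix I). Protocol 6.4, repeated in SAP 4.3.4, stops further vaccination for ineligibility that arises during the trial and makes no exception for the 4.4 deferrals. SAP 4.4.5 expects dose 2 within 28 days either side of the scheduled visit.

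**The concern.** A time-limited condition is handled as a permanent one. A girl with a recent live vaccine or transfusion would lose dose 2, although a short wait would remove the reason. The clearest case is a live vaccine in the 4 weeks after dose 1. It meets criterion 5 during the dosing period and so, on the literal text, bars a dose due 6, 12 or 24 months after the first.

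The girl then has one dose of a two-dose regimen, and Protocol 6.6 says no HPV mass campaign is planned in either country. The trial loses her sample one month after dose 2, which the per-protocol primary analysis requires (Protocol 11.4.3). She is not replaced (SAP 4.4.2). The two sites could also apply the text differently.

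**Working it through.** **Text against text**

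| Condition | Permanent bar in 4.4? | Deferral route in 4.4? |
|---|---|---|
| Fever (criterion 1) | No, exempted | Yes |
| Acute disease without fever (criterion 1) | Yes | Yes: contradiction |
| Blood products (criterion 4) | Yes | No |
| Live virus vaccine (criterion 5) | Yes | No |

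**How soon each condition lapses**

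Inputs: scheduled dose-2 days and ±28-day windows (Protocol 6.2 and Appendix I); 4 weeks = 28 days; 3 months taken as 90 to 92 days (assumption).

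- *Live vaccine after dose 1.* Latest day that counts: 1 + 28 = Day 29. Four weeks later: 29 + 28 = Day 57.
- *Live vaccine before dose 2.* If given on or before the scheduled day, it clears by day +28 at the latest, the last day of the window.
- *Blood products given d days before the scheduled day.* They clear (90 to 92) − d days after it. This is inside the window if (90 to 92) − d ≤ 28, that is, d ≥ 62 to 64. At worst (d = 0) they clear at +90 to +92, which is 62 to 64 days after the window closes.

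| Groups | Scheduled dose 2 | Earliest | Days from Day 57 to earliest | Latest blood-product clearance (d = 0) |
|---|---|---|---|---|
| 1 and 4 | Day 180 | 152 | 152 − 57 = 95 | Day 270 to 272 |
| 2 | Day 365 | 337 | 337 − 57 = 280 | Day 455 to 457 |
| 3 and 5 | Day 730 | 702 | 702 − 57 = 645 | Day 820 to 822 |

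**Whether power is at stake**

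The plan's own figure comes first. Inputs from Protocol 11.3: one-sided alpha 0.025/3 = 0.0083, SD 0.65 on the log10 scale, margin 0.5 (δ = 0.301), 95% power per serotype. A true ratio of 1 is assumed.

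n = 2σ²(z₁₋α + z₁₋β)²/δ² = 2 × 0.65² × (2.394 + 1.645)²/0.301² ≈ 152.1, so 153 evaluable per arm. Inflated, 153/(0.85 × 0.90) = 200, or 153/0.75 = 204. The stated 205 is consistent with both.

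At 205 × 0.85 × 0.90 = 156.8 evaluable per arm, power is 95.6% per serotype. Squaring, as the plan does, gives 91.4% for both. The documents give no rate for dose 2 lost under criteria 4 or 5. Over an assumed range of loss beyond the planned dropout, equal in both arms:

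| Extra loss | Power, both serotypes |
|---|---|
| 1% | 91.0% |
| 2% | 90.7% |
| 5% | 89.4% |
| 10% | 87.0% |

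The 15% dropout allowance is already 0.15 × 205 = 30.75, about 31 girls per arm. Losses within it change nothing.

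**The case against.** The strongest reply is that sensible sites would not apply the text this way.

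- Acute disease is expressly deferred in the second list, which defines it as illness with or without fever. The specific rule would prevail. This stands: that part is a drafting slip with one obvious resolution.
- Criteria 4 and 5 are defined relative to a dose, so booking dose 2 later means the look-back is no longer met, and for a live vaccine the ±28-day window usually suffices. This stands in part. Rebooking cannot undo a live vaccine already given in the 4 weeks after dose 1, and 4.4 acts on detection, with no instruction to rebook.
- The out-of-window sentence might seem to help. It sits in the paragraph limited to acute illness and gastroenteritis and does not lift the absolute bar.
- A deferred blood-product dose could fall as late as Day 270 to 272 in Groups 1 and 4, outside SAP 4.4.5. The Data Review Meeting could then exclude the girl from the per-protocol set. This stands: deferral may not recover her primary-analysis sample.
- The cost to the girl may be smaller than it looks. Protocol 1.1 cites data suggesting substantial protection from one dose, and Protocol 5.2.1 says Gardasil is licensed in both countries. A sponsor may also prefer a cautious bar. These points lower the stakes without making the text consistent.

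A reader might also infer from Protocol 6.6 that the priority vaccines it names cost a girl dose 2. The documents do not support that. Rabies, tetanus and COVID-19 vaccines are not on criterion 5's list; only the residual category of other vaccines could overlap. The only consequence 6.6 states is recording on the concomitant medication form.

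**Conclusion.** The point holds as a minor defect in a stated rule. On its literal text, 4.4 permanently bars dose 2 for two exclusions that lapse with time, and it contradicts itself on acute disease. The live-vaccine part has the clearest remedy: clearance always precedes the earliest dose 2 after a post-dose-1 vaccine, and falls inside the window for a vaccine given up to the scheduled day. For blood products the gain is mainly that the girl completes her regimen.

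A reader might infer that the trial is underpowered or its conclusions at risk, or that girls are already losing doses. Neither follows. There is no event rate, no sign of how sites apply the text, and power for both serotypes stays near 90% unless extra loss approaches 5%. The timing rests on 4 weeks as 28 days and 3 months as 90 to 92 days. The power figures assume a true ratio of 1 and independent serotypes.

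**What to change.** 1. Protocol 4.4, first list: replace the fever-only exemption with '(except fever, acute disease, or time-limited criterion 4 or 5, which are temporary deferments)'.
2. Protocol 4.4, deferral list and closing paragraph: add live virus vaccine within 4 weeks before dose 2, with dose 2 given once 4 weeks have passed. State that a live vaccine in the 4 weeks after dose 1 is a recorded deviation that does not bar dose 2.
3. In the same places, add blood products other than immune globulin within 3 months, using the existing out-of-window discretion with a deviation filed. Note that doses beyond ±28 days go to the Data Review Meeting and may be excluded from the per-protocol analysis. Immune globulin stays out because criterion 8 names it separately, counted from six months before dose 1, so that part of criterion 4 remains barred.
4. Protocol 6.4 and SAP 4.3.4, ineligibility bullet: add '(except the temporary deferments in Protocol 4.4)'.

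The bars for significant intercurrent illness and for investigator concern stay as they are.

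The cost is a short protocol amendment with advance written approval from all ethics committees and the sponsor (Protocol 13.1), one SAP line and a site memo. No procedures, samples or participants are added. The value depends on how many dose-2 visits remain, which the documents do not state. Bundling it with another amendment would be reasonable.

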### 4.5 Screen Failures

Screen failures are participants who consent to participate in the trial but are not subsequently enrolled in the study as they do not meet the inclusion/exclusion criteria. Individuals who are screen failures due to an acute illness at the time of screening maybe rescreened once the acute illness has resolved and if study participation does not increase any risk to the subject in the opinion of the clinical investigator. Rescreened participants should be assigned the same participant number as for the initial screening. Screen failures will be referred to a proper place for treatment outside of the study, as warranted.

# 5 STUDY PRODUCT/S

# 5.1 Study Vaccine

### 5.1.1 Product Description

Cecolin® is a mixture of two aluminum hydroxide adjuvant absorbed recombinant L1 capsid proteins of human papillomavirus (HPV) type-16 and type-18 each self-assembled into virus-like particles (VLPs). The HPV-16 and HPV-18 L1 antigens are expressed in Escherichia coli by recombinant DNA technology.

### 5.1.2 Manufacturer

Cecolin® is manufactured by Xiamen Innovax Biotech Co. Ltd., in Xiamen, China.

### 5.1.3 Presentation and Formulation

Recombinant plasmids containing the HPV 16 or 18 L1 genes were transferred into E.coli.

The vaccine lot for the clinical trial was produced

under the good manufacturing practice conditions according to the requirements of the China Food and Drug Administration.

Cecolin® is presented as 0.5 mL suspension for injection in a single-dose vial. Upon storage, a fine white deposit with a clear colorless supernatant can be observed. Cecolin® is a suspension after thorough agitation.

# 5.1.4 Stability and Storage

Cecolin® must be stored refrigerated at 2°C to 8°C (36°F and 46°F) and protected from light. Do not freeze. Discard if vaccine has been frozen. Cecolin® will be stored in monitored, temperature-controlled fridge with back-up power supply.

### 5.2 Control Vaccine

# 5.2.1 Product Description

Gardasil®, Human Papillomavirus Quadrivalent (Types 6, 11, 16, and 18) Vaccine, Recombinant, is a non-infectious recombinant quadrivalent vaccine prepared from the purified virus-like particles (VLPs) of the major capsid (L1) protein of HPV Types 6, 11, 16, and 18. Gardasil® is locally licensed in Bangladesh and Ghana.

### 5.2.2 Manufacturer

Gardasil® is manufactured by Merck Sharp Dohme, Inc.

### 5.2.3 Presentation and Formulation

The L1 proteins are produced by separate fermentations in recombinant Saccharomyces cerevisiae and self-assembled into VLPs. The fermentation process involves growth of *Saccharomyces cerevisiae* on chemically defined fermentation media which include vitamins, amino acids, mineral salts, and carbohydrates. The VLPs are released from the yeast cells by cell disruption and purified by a series of chemical and physical methods. The purified VLPs are adsorbed on preformed aluminum-containing adjuvant (Amorphous Aluminum Hydroxyphosphate Sulfate). The quadrivalent HPV VLP vaccine is a sterile liquid suspension that is prepared by combining the adsorbed VLPs of each HPV type and additional amounts of the aluminum-containing adjuvant and the final purification buffer.

Gardasil® is a suspension for intramuscular administration available in 0.5-mL single dose vials and prefilled syringes. Each 0.5-mL dose contains approximately 20 mcg of HPV 6 L1 protein, 40 mcg of HPV 11 L1 protein, 40 mcg of HPV 16 L1 protein, and 20 mcg of HPV 18 L1 protein.

Each 0.5-mL dose of the vaccine contains approximately 225 mcg of aluminum (as Amorphous Aluminum Hydroxyphosphate Sulfate adjuvant), 9.56 mg of sodium chloride, 0.78 mg of L-histidine, 50 mcg of polysorbate 80, 35 mcg of sodium borate, <7 mcg yeast protein/dose, and water for injection. The product does not contain a preservative or antibiotics.

After thorough agitation, Gardasil® is a white, cloudy liquid.

### 5.2.4 Stability and Storage

Gardasil® must be stored refrigerated at 2 to 8°C (36 to 46°F) and protected from light. Do not freeze.

Gardasil® should be administered as soon as possible after being removed from refrigeration. Gardasil® can be out of refrigeration (at temperatures at or below 25°C/77°F), for a total time of not more than 72 hours. Gardasil® will be stored in monitored, temperature-controlled fridge with back-up power supply.

### 5.3 Dose Preparation and Administration

In this open-label study, the vials of Cecolin® and Gardasil® vaccine will be labeled with the licensed product labels. It will be labeled with the following minimum information: name of the medicinal product, route of administration, expiry date, lot number, dose volume, and a cautionary statement ("For Clinical Trial Use Only"). Dose preparation and administration for each vaccine will be completed according to manufacturer recommendations and carried out by qualified study staff members with preparation witnessed by another study staff member. Vaccine vials will be labeled with the participant's study number for monitoring purposes. 0.5 mL of Gardasil® will be withdrawn from the single-dose vial using a sterile needle and syringe and use promptly.

Cecolin® and Gardasil® are injected intramuscularly and the preferred site for vaccination is deltoid muscle of upper arm.

Cecolin® should be shaken well before use, and it should be a white homogeneous suspension after shaking. A separate sterile auto-disabled syringe and needle must be used for each vaccination. Cecolin® should be administered as soon as possible after removal from the refrigeration container. Any vial with crack, label unclear or invalid and vaccine with abnormal appearance should not be used.

# 5.4 Accountability and disposal

The Site Principal Investigator (PI) is responsible for ensuring study product distribution and disposition and has ultimate responsibility for study product accountability. The Site PI will delegate to a Site Research Pharmacist responsibility for study product accountability. Study product accountability records should include date received, date administered, product administered, treatment assignment, and the subject identification number to whom the study product was administered. The designated Site Research Pharmacist(s) will be responsible for maintaining accurate records of the shipments and dispensing the investigational vaccine product. The pharmacy records must be available for inspection by the CRO clinical monitor and is subject to inspection by the local regulatory agency at any time. Used and unused vaccine vials will be retained until monitored and released for disposition per PATH and local regulatory agencies, but syringes and other dry materials used will be destroyed per site SOPs immediately following study vaccinations.

It is the responsibility of pharmacist to ensure that vaccine has not been exposed to temperatures outside the allowed range during transport or storage at the facility prior to being dispensed for vaccination. Should there be a deviation outside the allowed temperature range, the affected

vaccine(s) will be quarantined. The temperature deviation will be reported to the CRO who will advise on the action to be taken based on the magnitude and duration of the temperature deviation.

